8.1.6 Demographic and clinical parameters

For all sub studies, demographic and clinical information are obtained from medical records and patient interviews (sub studies 1 and 3) or Diabetesdatabasen (sub study 2). The following clinical information is registered:

Demographic information:

- Age and sex
- Height and weight
- Body mass index

Information on chronic pancreatitis:

- Duration and aetiology
- Smoking and drinking history
- Complications including exocrine pancreatic insufficiency and pain
- Treatment (medical treatment including pancreatic enzyme replacement therapy, history of endoscopic treatment or surgery)

Information on diabetes:

- Duration of diabetes
- Information on past hypoglycaemic episodes according to the ADA definitions of hypoglycaemia²¹
- Presence of micro- and macrovascular complications
- Glucose lowering therapy including insulin regime and daily insulin units
- HbA1c and other relevant biochemical parameters in Diabetesdatabasen (sub study 2 only)

Information on comorbidity is registered using the Charlson Comorbidity index.

Information on demographic and clinical parameters including comorbidities are registered for two reasons: First, the information is obtained to ensure the suitability of the subjects in relation to inclusion in the study. Second, the information must be used for later analysis in an anonymized form.

8.2 Data management

The study will be submitted to the Northern Region of Denmark (“Forskningsanmeldelse Region Nordjylland – Registrering af forskningsprojekter”). Standard operating procedures (SOPs) for data handling and record keeping exists within the research centres and these will be followed. The principal investigator must maintain complete and accurate records to ensure that study execution is fully documented, and the study data can be subsequently verified. REDCap, a secure browser-based software, will be used for filling an electronic case report form for each participant (sub studies 1 and 3). REDCap meets all regulatory safety requirements and is approved for data collection by the North Danish Region. Data recording will begin when a participant is included and will occur gradually to the end of the study. Any corrections will be made in such a way that information from the original version is still available. Putative changes are endorsed by initials and date. All forms are filled out during (or immediately after) the assessment of a participant and must be legible. Data will be stored at Aalborg University Hospital, Department of Gastroenterology and Hepatology, for a minimum of 5 years after the study has ended. Relevant information from the participants’ medical records will be given to the investigator if needed to assess the in- and

exclusion criteria. After five years all data will be anonymized. The principal investigator allows direct access to all source data and documents at monitoring, auditing, and inspection from the competent authorities. A participant identification list is created for all persons included in the study. This list contains patient number, full name, and civil registration number. The list is populated and updated by a study nurse or other competent person and is stored at Department of Gastroenterology, Aalborg University Hospital.

8.2.1 Case report forms

All data from sub studies 1 and 3 are entered directly into electronic CRFs using REDCap, licensed by Aalborg University Hospital, and saved electronically. All forms are filled out during (or immediately after) the assessment of a subject and must be legible. Errors and corrections are logged as provided by the REDCap interface. It is possible to export validated data from REDCap to e.g., a statistical program (e.g., STATA) for further statistical analysis. When data have been entered, reviewed, and verified the data will be frozen to prevent editing. Digitalized data are backed up and stored on specific drives at each site under the responsibility of the principal investigators for a minimum of 5 years after the study has ended.

8.2.2 Source data identification and protection

Patient Identification List containing patient number, full name, civil registration number for all participants included in sub studies 1 and 3 are created, and ethics according to "databeskyttelsesforordningen" and "databeskyttelsesloven" is ensured. The list is populated and updated by a project nurse or other competent person. A list of all source documents will be devised at the initiation of the study. All source documentation will be stored on a secure drive under the responsibility of the principal investigator.

8.3 Plan for statistical analyses

8.3.1 Statistical methods

- **Sub study 1:** CGM metrics collected in periods with monitoring using CGM vs. SMBG are compared using multiple linear regression models. Further, regression models are fitted to investigate associations between baseline characteristics and measures of glucose variability.
- **Sub study 2:** HbA1c variability metrics are compared between PPDM and type 2 diabetes patients using multiple linear regression models. Hb1Ac level trajectories are visually characterized and latent class analysis is used to define distinct patient clusters.
- **Sub study 3:** Prevalence estimates of hypoglycaemia are reported as point prevalence estimates with 95% confidence intervals. Logistic and Poisson regression models are fitted to investigate associations between patient characteristics and hypoglycaemia risk.

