6.3 Hypotheses

- **Sub study 1:** Short-term glucose variability and time in hypoglycaemia, as determined by CGM, is increased in patients with PPDM compared to a matched group of individuals with type 2 diabetes; the use of CGM will lead to decreased time in hypoglycaemia compared to SMBG in PPDM patients.
- **Sub study 2:** Long-term glucose variability, as determined by visit-to-visit HbA1c, is increased in patients with PPDM compared to a matched group of individuals with type 2 diabetes.
- **Sub study 3:** Patients with PPDM report high frequencies of self-reported hypoglycaemic events and targetable risk factors for hypoglycaemia can be identified.

7. Methods I: design, setting, participants, and outcomes

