7.1 Study designs

- **Sub study 1** is a prospective open-label crossover randomized controlled study of the effect of CGM on hypoglycaemia compared to SMBG in PPDM patients
- **Sub study 2** is a retrospective cohort study of long-term glucose variability, as determined by visit-to-visit HbA1c levels, in PPDM patients compared to matched individuals with type 2 diabetes
- **Sub study 3** is a multicentre cross-sectional study based on patient-reported outcomes (PROs)

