7.6 Outcomes

7.6.1 Primary endpoints

- **Sub study 1:** Difference (monitoring with CGM vs. SMBG) in time spent with glucose value <3.0 mmol/L (level 2 hypoglycaemia) during the last two weeks of each study period
- **Sub study 2:** Long-term glucose variability (up to 48 months) expressed as difference in visit-to-visit HbA1C VIM (Variability Independent of the Mean) between PPDM patients and individuals with type 2 diabetes patients
- **Sub study 3:** Proportions of patients with severe hypoglycaemia during the preceding 12 months. Hypoglycaemic endpoints are defined according to the latest ADA recommendations²¹

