7.6.2 Secondary endpoints

Sub study 1:

- Short term (20 days) difference in CGM metrics between PPDM patients and individuals with type 2 diabetes
- CGM time in range (glucose value >3.9 mmol/L and ≤10 mmol/L)
- CGM time below range (glucose value ≤3.9 mmol/L)
- CGM time above range (glucose value >10 mmol/L)
- CGM metrics of glucose variability (SD (Standard deviation) and CV (Coefficient of Variance) of mean glucose, mean amplitude of glycaemic excursions [MAGE] and continuous overall net glycaemic action [CONGA])

Sub study 2:

- Difference in HbA1C CV between PPDM and type 2 diabetes patients during up to 48 months follow-up
- Difference in HbA1C average real variability between PPDM and type 2 diabetes patients during up to 48 months follow-up
- Difference in HbA1C level trajectories between PPDM and type 2 diabetes patients during up to 48 months follow-up

Sub study 3:

- Risk factors for hypoglycaemia including demographics and routine clinical and biochemical parameters
- Awareness of hypoglycaemia based on the Clarke hypoglycaemia awareness survey
- Proportions of patients with ketoacidosis during the preceding 12 months

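### Sub study 2 makes the PPDM versus type 2 diabetes difference in HbA1c trajectories a secondary endpoint, but the methods named for it give at most an informal comparison and no estimated difference

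*Protocol*

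**What the plan says.** Sub study 2 is comparative by design. Protocol section 7.1 describes it as a retrospective cohort study of HbA1c variability "in PPDM patients compared to matched individuals with type 2 diabetes".

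It has four endpoints. The primary one (7.6.1) is the between-group difference in VIM of visit-to-visit HbA1c. The three secondary ones (7.6.2) are each worded as a contrast of the two groups. Two of them concern measures of spread, namely the CV and the average real variability of HbA1c. The remaining one concerns the course of HbA1c itself: "Difference in HbA1C level trajectories between PPDM and type 2 diabetes patients during up to 48 months follow-up".

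Section 8.3.1 gives sub study 2 two sentences. The first is on the measures of spread: "HbA1c variability metrics are compared between PPDM and type 2 diabetes patients using multiple linear regression models". The second turns to trajectories and names neither group: "Hb1Ac level trajectories are visually characterized and latent class analysis is used to define distinct patient clusters".

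**The concern.** The endpoint asks how far the HbA1c course in PPDM differs from that in type 2 diabetes. The method asks which courses exist among the patients. These are different questions, and an answer to the second does not supply the first.

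A report that follows 8.3.1 to the letter would show curves and a set of clusters for this endpoint. A reader could form an impression of the contrast but would have no effect size and no interval. Any formal comparison added after the data had been seen would be a choice the plan had not fixed. There are several such choices, and they can lead to different conclusions.

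**Working it through.** The point turns on text, so there is no figure in the plan to reproduce. The check maps each sub study 2 endpoint to the method that 8.3.1 gives it.

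| Endpoint | Section | Between-group method in 8.3.1 |
|---|---|---|
| VIM (primary) | 7.6.1 | Multiple linear regression |
| CV | 7.6.2 | Multiple linear regression |
| Average real variability | 7.6.2 | Multiple linear regression |
| Level trajectories | 7.6.2 | Plots and latent classes; no group contrast named |

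Count: 3 of 4 endpoints have a named between-group estimate and 1 of 4 does not. Among the secondary endpoints it is 1 of 3.

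**Does the regression sentence reach the trajectories?** No. Its subject is variability metrics, each of which reduces a patient's HbA1c series to a single number for its spread. A level trajectory is the course of HbA1c over time, and the protocol treats it in a separate sentence.

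**Do the plots give the contrast?** Only informally, and only if drawn by diabetes type, which 8.3.1 does not say. A plot by group is a descriptive comparison without an estimated difference.

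**Do the latent classes give the contrast?** Not on their own. Latent class analysis sorts patients by the shape of their course. It compares PPDM with type 2 diabetes only if class membership is then related to diabetes type, or if diabetes type enters the model for membership. Neither step is stated. Nor is it stated that both groups are fitted together, which is needed for the classes to mean the same thing in each group.

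**Does another section supply it?** No. Section 8.3.3 leaves missing data to the final statistical analysis plan, and no section says that the trajectory comparison is left to it.

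**Is the hypothesis touched?** No. Section 6.3 states it in terms of variability: "Long-term glucose variability, as determined by visit-to-visit HbA1c, is increased in patients with PPDM". The regression on VIM, CV and average real variability addresses it.

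**The case against.** The strongest reply is that this is detail for the analysis plan. Section 8.3.1 is brief for every sub study, a final plan is mentioned and is not shown, and how classes or curves are related to diabetes type is the sort of thing such a plan settles. The endpoint and the design already fix the two groups, and the preceding sentence names both. The natural reading is therefore that trajectories will be shown for each group. Plots and latent classes are legitimate trajectory methods, and the endpoint's wording does not demand a test.

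Much of this stands. It rules out the inference that the groups would not be compared at all: plots by group would allow an informal comparison, and the plan not shown may add a formal one. It also means that latent class analysis is not a wrong choice.

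It does not remove the mismatch. The protocol did name a method for this endpoint, and as written that method answers a different question. For the other three endpoints the protocol names the comparison in the same two-sentence space.

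A reader might also infer that a mixed model should replace the latent classes. That is not supported. A contrast of mean slopes can miss subgroups in PPDM whose courses run in opposite directions and cancel, which is what latent classes can show. A class comparison has less power when all patients shift by a similar amount. Each sees what the other can miss.

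**Conclusion.** The point holds and is minor. One of four sub study 2 endpoints, and one of three secondary ones, is defined as a between-group difference but has no named method that estimates that difference with its uncertainty. The methods given allow at most an informal comparison.

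Two stronger conclusions are tempting. The first is that the main result of sub study 2 is compromised. It is not: the primary endpoint and the hypothesis have a named between-group regression. The second is that a definite amount of power is lost. The protocol cannot support such a figure. Section 7.8 expects at least 75 PPDM cases, but the protocol gives no number of type 2 comparators, no matching ratio, no number of HbA1c tests per person and no variances. Any power figure would rest on assumed values for all of these.

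The verdict rests on the protocol text alone and would lapse if the final analysis plan already states the comparison.

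**What to change.** Add to the sub study 2 entry in 8.3.1, in words such as these:

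> Trajectories are plotted by diabetes type. One latent class model is fitted to both groups together, and class membership is compared by diabetes type with a 95% confidence interval. The group difference over time is estimated with a linear mixed model for repeated HbA1c (group, time, group-by-time, random intercept and slope), accounting for the matching, and is reported with a 95% confidence interval.

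If time is modelled as a curve, a single slope difference no longer describes the contrast. The plan should then give a joint group-by-time test and the group difference at times fixed in advance, for example 12, 24, 36 and 48 months.

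Both analyses should be reported whatever they show, with neither placed above the other. If the investigators want only a description, rewording the endpoint in 7.6.2 as descriptive would also remove the mismatch, at the price of giving up the estimate.

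Cost: a few sentences and one extra model on HbA1c values already extracted. The planned latent class analysis stays. The change is best made before the analysis, since 8.3.4 requires departures from the statistical plan to be reported.

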7.8 Sample size considerations

- **Sub study 1:** The sample size calculation is based on the primary endpoint described for sub study 1 (time in level 2 hypoglycaemia). A sample size of 24 patients is determined to have at least 80% power to detect a reduction in the percentage of time spent with a glucose value <3.0 mmol/l (level 2 hypoglycaemia), assuming a relative treatment reduction of 50% from a percentage of time spent with glucose value <3.0 mmol/l of 3%, standard error of 2.5%, and type I error rate (2 sided) of 5%. To account for approximately 25% dropouts, the final sample size is set to 30 patients. As there are currently no adequate data on CGM in patients with pancreatogenic diabetes to inform sample size calculations, assumptions are based on findings in older adults with long-standing type 1 diabetes who have an increased risk of hypoglycaemia⁷.
- **Sub study 2:** This is a retrospective cohort study based on data already collected in Diabetesdatabasen and the sample size will therefore be dictated by the number of individuals in the

database. Previous population-based studies from our group have shown that the proportion of patients with PPDM among patients clinically diagnosed type 1 or type 2 diabetes is approximately 1.5%^{4,22}. In Diabetesdatabasen there are currently >5000 unique adult individuals registered, and thus we expect to identify at least 75 PPDM cases which should provide sufficient statistical power to the planned analyses according to a previous study from our group²².

- **Sub study 3:** This is a cross-sectional survey. No previous studies have evaluated the prevalence of self-reported severe hypoglycaemia and related risk factors in patients with PPDM. However, according to recent population-based registry data from our group, patients with PPDM have a risk of hospitalization for hypoglycaemia comparable to that observed for individuals with type 1 diabetes (*unpublished data*). In type 1 diabetes, the yearly prevalence of self-reported severe hypoglycaemia range between 10–53%²³. Thus, we consider a sample size of 200 patients will provide sufficient power to obtain prevalence estimates with reasonable precision and allow for multivariate modelling of putative risk factors associated with severe hypoglycaemia.

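### Does naming Poisson regression for the hypoglycaemia risk factors in sub study 3 commit the trial to wrong standard errors?

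*Protocol*

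**What the plan says.** Protocol section 8.3.1 gives sub study 3 two sentences. The first covers the prevalence: "Prevalence estimates of hypoglycaemia are reported as point prevalence estimates with 95% confidence intervals". The second covers the risk factors: "Logistic and Poisson regression models are fitted to investigate associations between patient characteristics and hypoglycaemia risk". It does not say which outcome belongs to which model, how standard errors are obtained, or what happens if counts are overdispersed.

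The primary endpoint of sub study 3 (section 7.6.1) is "Proportions of patients with severe hypoglycaemia during the preceding 12 months", a yes/no outcome per patient. The risk-factor analysis is a secondary endpoint (section 7.6.2): "Risk factors for hypoglycaemia including demographics and routine clinical and biochemical parameters". The other two secondary endpoints are awareness on the Clarke survey and the proportion with ketoacidosis. Event frequency appears in the hypothesis (section 6.3): "Patients with PPDM report high frequencies of self-reported hypoglycaemic events".

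Section 7.8 sets the sample at 200, expected to give reasonable precision for the prevalence and to "allow for multivariate modelling of putative risk factors associated with severe hypoglycaemia". Section 8.3.3 refers to a final statistical analysis plan, which is not at hand.

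**The concern.** A Poisson model takes the variance of the outcome to equal its mean. Hypoglycaemic episodes tend to recur in the same patients, and the protocol's introduction itself describes unstable diabetes with frequent episodes. Counts over 12 months would then vary more than a Poisson model allows, and its default confidence intervals would be too narrow. If the Poisson model is instead meant for the yes/no outcome, as is often done to obtain prevalence ratios, the default variance is too large and real associations are harder to detect. Section 8.3.1 mentions no correction for either case.

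Finding targetable risk factors is the second half of the sub study 3 hypothesis, and section 9.1 foresees using such results to direct patients to specialised clinics. If many characteristics are screened with intervals that are too narrow, chance findings could be taken for risk factors.

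**Working it through.** The plan states no standard error, dispersion or error rate for the Poisson model, so there is no figure of its own to reproduce. Two things can be checked: how large the error would be if default standard errors were used, and whether the protocol commits to them.

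**Inputs from the protocol.** n = 200 (section 7.8) and a prevalence between 10% and 53%, borrowed from type 1 diabetes: "the yearly prevalence of self-reported severe hypoglycaemia range between 10–53"% (section 7.8). **Assumptions.** A two-sided 5% test; a characteristic with no effect that splits the patients 100/100; for counts, a negative binomial distribution. The protocol gives no event rate or dispersion. The 30% prevalence is an illustrative value inside the range.

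**Yes/no outcome.** The Poisson model uses variance p, while the true variance is p(1 − p). The ratio of default to true standard error is 1/√(1 − p), and the actual test level is 2·[1 − Φ(1.96/√(1 − p))].

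| p | SE ratio | Actual level | Simulated (2,000 runs) |
|---|---|---|---|
| 10% | 1/√0.90 = 1.05 | 3.9% | 3.8% |
| 30% | 1/√0.70 = 1.20 | 1.9% | 2.1% |
| 53% | 1/√0.47 = 1.46 | 0.4% | 0.4% |

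This error is conservative. It cannot produce the excess of false risk factors that is feared.

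**Event counts.** With negative binomial shape k, the chance of no event is (1 + mean/k)^(−k). Setting this to 1 − p gives a variance/mean ratio φ = (1 − p)^(−1/k). The default standard error is 1/√φ of the true one, and the actual level is 2·[1 − Φ(1.96/√φ)].

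| p | k (assumed) | φ | Actual level | Simulated (10,000 runs) |
|---|---|---|---|---|
| 10% | 1.0 | 1.11 | 6.3% | 4.8% |
| 10% | 0.3 | 1.42 | 10.0% | 9.1% |
| 10% | 0.1 | 2.87 | 24.7% | 23.9% |
| 30% | 1.0 | 1.43 | 10.1% | 9.9% |
| 30% | 0.5 | 2.04 | 17.0% | 16.8% |
| 30% | 0.3 | 3.28 | 27.9% | 27.4% |
| 53% | 1.0 | 2.13 | 17.9% | 18.2% |
| 53% | 0.5 | 4.53 | 35.7% | 35.5% |

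A second set of simulations fixed the mean count instead, at 0.2 to 1.5 events per year (also an assumption). It gave 13% to 42% at 30% to 53% prevalence, and 25% to 58% at 10% prevalence. Over both sets the level runs from about 5% to 58%. The assumed dispersion drives that spread, and nothing in the protocol narrows it.

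**What the protocol commits to.**

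- Section 8.3.1 names a model family. A Poisson model with a robust (sandwich) variance is still Poisson regression and satisfies the sentence. In simulation it brings the yes/no case to 4.3%, 5.2% and 4.6% at 10%, 30% and 53% prevalence.
- The primary endpoint in section 7.6.1 is yes/no. Logistic regression is named in the same sentence, and its binomial variance is correct for that outcome.
- Neither section 7.6.1 nor section 7.6.2 lists a number of events per patient as an endpoint for sub study 3. The outcome on which the inflation depends is therefore not specified.
- The two faults exclude each other for any one outcome. The protocol does not say that either situation arises with default errors.

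**The case for a change.** The strongest counter-argument is that section 8.3.1 is headed as the plan for statistical analyses and does name Poisson. Only missing data are expressly deferred to the later plan (section 8.3.3). A move to negative binomial regression would change the named model and, under section 8.3.4, would have to be reported as a deviation. Counts are also not far-fetched: the hypothesis speaks of frequencies of events, and section 8.1.6 has past hypoglycaemic episodes recorded. The arithmetic is right in both directions, and for clustered counts the inflation could be large.

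The arithmetic stands. So does one caution: a robust variance does not fully repair sparse, strongly clustered counts. At 10% prevalence with 200 patients the simulated level was still 8% to 10%, against 4.6% to 6.7% at 30% to 53%.

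What does not stand is the step from these facts to an error in the protocol. The statistical analysis plan can specify a robust variance without contradicting section 8.3.1. The choice of variance estimator and the check for overdispersion are normally settled in that plan, whether or not the protocol says so topic by topic. With one or two sentences per sub study, section 8.3.1 is plainly a summary.

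**Conclusion.** The concern does not hold. The protocol neither prescribes default Poisson standard errors nor rules out corrected ones. It names a suitable model for its yes/no primary endpoint and lists no count endpoint for sub study 3. The potential errors are real but conditional on default standard errors being used. For a yes/no outcome a 5% test would then be conservative, at 3.9% to 0.4%. For counts it would run from about 5% to 58%, under event distributions assumed for the check and not taken from the protocol. Only a secondary analysis could be affected; the primary prevalence estimate with its 95% confidence interval does not depend on it. Which outcome the Poisson model serves, and how its variance is estimated, is for the statistical analysis plan to say. This conclusion rests on section 8.3.1 being read as written. It would change if that plan, which is not at hand, analysed event counts with default Poisson errors.
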